### LABORATORY

PARAMETER	GRADE 1 MILD	GRADE 2 MODERATE	GRADE 3 SEVERE	GRADE 4 POTENTIALLY LIFE-THREATENING
HEMATOLOGY Standard International Units are listed in italics				
Absolute neutrophil count (ANC)	1.000 x 10^9 – 1.300 x 10^9/L	0.750 x 10^9 – 0.999 x 10^9/L	0.500 x 10^9 – 0.749 x 10^9/L	< 0.500 x 10^9/L
Fibrinogen, decreased	1.00 – 2.00 g/L OR 0.75 – 0.99 x LLN	0.75 – 0.99 g/L OR 0.50 – 0.74 x LLN	0.50 – 0.74 g/L OR 0.25 – 0.49 x LLN	< 0.50 g/L OR < 0.25 x LLN OR Associated with gross bleeding

LABORATORY				
PARAMETER	GRADE 1 MILD	GRADE 2 MODERATE	GRADE 3 SEVERE	GRADE 4 POTENTIALLY LIFE- THREATENING
Hemoglobin (Hgb)				
HIV POSITIVE ONLY	8.5 – 10.0 g/dL	7.5 – 8.4 g/dL	6.50 – 7.4 g/dL	< 6.5 g/dL
HIV NEGATIVE ONLY	10.0 – 10.9 g/dL OR Any decrease 2.5 – 3.4 g/dL	9.0 – 9.9 g/dL OR Any decrease 3.5 – 4.4 g/dL	7.0 – 8.9 g/dL OR Any decrease ≤4.5 g/dL	< 7.0 g/dL
Comment: The decrease is a decrease from baseline				
International Normalized Ratio of prothrombin time (INR)	1.1 – 1.5 x ULN	1.6 – 2.0 x ULN	2.1 – 3.0 x ULN	> 3.0 x ULN
Methemoglobin	5.0 – 10.0%	10.1 – 15.0%	15.1 – 20.0%	> 20.0%
Prothrombin Time (PT)	1.1 – 1.25 x ULN	1.26 – 1.50 x ULN	1.51 – 3.00 x ULN	> 3.00 x ULN
Partial Thromboplastin Time (PTT)	1.1 – 1.66 x ULN	1.67 – 2.33 x ULN	2.34 – 3.00 x ULN	> 3.00 x ULN
Platelets, decreased	$100.000 \times 10^9 - 124.999 \times 10^9/L$	$50.000 \times 10^9 - 99.999 \times 10^9/L$	$25.000 \times 10^9 - 49.999 \times 10^9/L$	< $25.000 \times 10^9/L$
WBC, decreased	$2.000 \times 10^9 - 2.500 \times 10^9/L$	$1.500 \times 10^9 - 1.999 \times 10^9/L$	$1.000 \times 10^9 - 1.499 \times 10^9/L$	< $1.000 \times 10^9/L$
CHEMISTRIES				
Acidosis	NA	pH < normal, but $\geq 7.3$	pH < 7.3 without life-threatening consequences	pH < 7.3 with life-threatening consequences
Albumin, serum, low	$30 \text{ g/L} - < LLN$	$20 - 29 \text{ g/L}$	$< 20 \text{ g/L}$	NA
Alkaline Phosphatase	$1.25 - 2.5 \times ULN^\dagger$	$2.6 - 5.0 \times ULN^\dagger$	$5.1 - 10.0 \times ULN^\dagger$	$> 10.0 \times ULN^\dagger$
Alkalosis	NA	pH > normal, but $\leq 7.5$	pH > 7.5 without life-threatening consequences	pH > 7.5 with life-threatening consequences
ALT (SGPT)	$1.25 - 2.5 \times ULN$	$2.6 - 5.0 \times ULN$	$5.1 - 10.0 \times ULN$	$> 10.0 \times ULN$
AST (SGOT)	$1.25 - 2.5 \times ULN$	$2.6 - 5.0 \times ULN$	$5.1 - 10.0 \times ULN$	$> 10.0 \times ULN$
Bicarbonate, serum, low	$16.0 \text{ mmol/L} - < LLN$	$11.0 - 15.9 \text{ mmol/L}$	$8.0 - 10.9 \text{ mmol/L}$	$< 8.0 \text{ mmol/L}$
Bilirubin (Total)	$1.1 - 1.5 \times ULN$	$1.6 - 2.5 \times ULN$	$2.6 - 5.0 \times ULN$	$> 5.0 \times ULN$
Calcium, serum, high	$2.65 - 2.88 \text{ mmol/L}$	$2.89 - 3.13 \text{ mmol/L}$	$3.14 - 3.38 \text{ mmol/L}$	$> 3.38 \text{ mmol/L}$
Calcium, serum, low	$1.95 - 2.10 \text{ mmol/L}$	$1.75 - 1.94 \text{ mmol/L}$	$1.53 - 1.74 \text{ mmol/L}$	$< 1.53 \text{ mmol/L}$

Cardiac troponin I (cTnI)	NA	NA	NA	Levels consistent with myocardial infarction or unstable angina as defined by the manufacturer
Creatine Kinase	3.0 – 5.9 x ULN†	6.0 – 9.9 x ULN†	10.0 – 19.9 x ULN†	≥□20.0 x ULN†
Creatinine	1.1 – 1.3 x ULN†	1.4 – 1.8 x ULN†	1.9 – 3.4 x ULN†	≥□3.5 x ULN†

Lipase	1.1 – 1.5 x ULN	1.6 – 3.0 x ULN	3.1 – 5.0 x ULN	> 5.0 x ULN
Lactate	ULN - < 2.0 x ULN without acidosis	ε2.0 x ULN without acidosis	Increased lactate with pH < 7.3 without life-	Increased lactate with pH < 7.3 with life-
Magnesium, serum, low	0.60 – 0.70 mmol/L	0.45 – 0.59 mmol/L	0.30 – 0.44 mmol/L	< 0.30 mmol/L
Pancreatic amylase	1.1 – 1.5 x ULN	1.6 – 2.0 x ULN	2.1 – 5.0 x ULN	> 5.0 x ULN
Phosphate, serum, low	0.81 mmol/L – < LLN	0.65 – 0.80 mmol/L	0.32 – 0.64 mmol/L	< 0.32 mmol/L
Potassium, serum, high	5.6 – 6.0 mmol/L	6.1 – 6.5 mmol/L	6.6 – 7.0 mmol/L	> 7.0 mmol/L
Potassium, serum, low	3.0 – 3.4 mmol/L	2.5 – 2.9 mmol/L	2.0 – 2.4 mmol/L	< 2.0 mmol/L
Sodium, serum, high	146 – 150 mmol/L	151 – 154 mmol/L	155 – 159 mmol/L	ε160 mmol/L
Sodium, serum, low	130 – 135 mmol/L	125 – 129 mmol/L	121 – 124 mmol/L	δ120 mmol/L
URINALYSIS Standard International Units are listed in italics				
Hematuria (microscopic)	6 – 10 RBC/HPF	> 10 RBC/HPF	Gross, with or without clots OR with RBC casts	Transfusion indicated
Proteinuria, random collection	1 +	2 – 3 +	4 +	NA
Proteinuria, 24 hour collection				
Adult	0.200 – 0.999 g/d	1.000 – 1.999 g/d	2.000 – 3.500 g/d	> 3.500 g/d

PARAMETER	GRADE 1 MILD	GRADE 2 MODERATE	GRADE 3 SEVERE	GRADE 4 POTENTIALLY LIFE-THREATENING
Glucose, serum, high				
Nonfasting	6.44 – 8.88 mmol/L	8.89 – 13.88 mmol/L	13.89 – 27.75 mmol/L	> 27.75 mmol/L
Fasting	6.11 – 6.94 mmol/L	6.95 – 13.88 mmol/L	13.89 – 27.75 mmol/L	> 27.75 mmol/L
Glucose, serum, low	3.05 – 3.55 mmol/L	2.22 – 3.06 mmol/L	1.67 – 2.23 mmol/L	< 1.67 mmol/L

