### 7.2 Secondary Objectives

Secondary objectives are to determine in HIV positive patients:

1. The safety profile of rosuvastatin
2. The effect of rosuvastatin on vessel wall function and biomarkers of atherosclerosis and innate immune activation
3. The effect of rosuvastatin on fasting lipids and glucose
4. Whether baseline measures of immune activation and inflammation predicts cIMT or progression of cIMT
5. Whether a change in measures of immune activation and inflammation from baseline after three months of rosuvastatin therapy predicts progression of cIMT

Secondary outcome measures include:

[figure not shown]
1. The rate of adverse effects (symptomatic and biochemical) between the two treatment arms
2. The effect of rosuvastatin on cIMT and cPWV
3. The effect of rosuvastatin on immunological and inflammatory markers (including sCD14, sCD163, neopterin, S-VCAM-1, adiponectin, CCL2, inflammatory (CD16+) monocyte expression of CD38, CX3CR1 and CD11b)
4. The effect of rosuvastatin on fasting total cholesterol, LDL, HDL, TG and glucose levels after 6, 12 and 24 months of therapy
5. The relationship between baseline measures of sCD14, sCD163, and neopterin and baseline cIMT
6. The relationship between baseline measures of sCD14, sCD163, and neopterin and rate of progression of cIMT
7. The relationship between change from baseline to 3 months in markers of immune activation and inflammation (sCD14, CCL2, and inflammatory (CD16+) monocyte phenotypic expression of CD38, CD11b) and progression of cIMT at 12 and 24 months.

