## **11.2 Laboratory Assessments**

### **Handling of Biological samples**

All biological samples (excluding those for storage and testing of innate immunity) will be processed at the Alfred Hospital laboratory or the Swiss site; local laboratory reference ranges will apply (see appendix 22.3 and 22.4).

Biological samples for testing of innate immunity will be handled at the Burnet Institute. Plasma will be separated and frozen (-80°C). Plasma markers will be analysed on batched frozen samples by ELISA.

Swiss sites will store plasma samples (6mls per visit) at -80°C and ship to the HUG cardiology laboratory for testing of plasma markers. Innate immunity markers (PBMC) will not be performed at Swiss sites.

A separate laboratory SOP will be provided to all the Swiss sites.

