### **Laboratory assessments for safety**

Routine laboratory assessments for safety and tolerability will be performed including:

- Full Blood Examination (FBE)
  - o Consisting of; Haemoglobin (Hb), total White Cell Count (WCC), Lymphocyte Count (Lymp), Neutrophil Count (Neut) and Platelet count (Plt)
- Biochemistry
  - o Consisting of; Sodium (Na), Potassium (K+), Chloride (Cl), Bicarbonate (HCO3), Calcium (Ca), Phosphate (PO4), Urea (Ur), Creatinine (Cr) and creatinine phosphokinase (CPK)

- An estimated glomerular filtration rate (eGFR) based on the Modification of Diet in Renal Disease (MDRD) equation is calculated electronically by the AH laboratory and will be recorded
- Liver Function Tests: Total Protein (TP), Albumin (Alb), Bilirubin (Bil), Alanine aminotransferase (ALT), Alkaline phosphatase (ALP) and Gamma-glutamyl transpeptidase (GGT)
- Pregnancy screen in women with child bearing potential (at screening visit); Beta Human chorionic gonadotrophin ( $\beta$ -HCG)

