## **13 Adverse Events**

An AE is defined as follows:

Any untoward medical occurrence in a clinical investigation subject administered a medicinal product and which does not necessarily have a causal relationship with this treatment. An AE can therefore be any unfavourable and unintended sign, symptom, or disease temporally associated with the use of a medicinal product, whether or not considered related to the medicinal product.

Pre-existing or recurrent conditions that occur during the study should not be considered as AEs unless they change in frequency or severity.

All AEs that occur from the time the subject consents to participate in the study and throughout the duration of the study shall be recorded as an AE in the individuals CRF.

At the final study visit (week 96) any ongoing adverse events deemed related to study drug will be followed up for a minimum of 30 days and until resolution.

In case a treatment interruption is needed during the treatment period in the event of a suspected toxicity, the subject will not automatically be withdrawn from the trial, as long as treatment interruption does not exceed 4 weeks.

AEs and SAEs will be categorised and recorded as per the modified Division of AIDS table for grading the Severity of Adverse Events (see Appendix 22.6). Causal relationship of AEs and SAEs to the trial and the study medication will also be assessed.

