## 15 Data safety and monitoring board

An independent Data safety and monitoring board (DSMB) will be set up to monitor the safety of and efficacy in the participants enrolled in the trial. The DSMB will be chaired by [name]. Members will include one cardiologist from Switzerland (Proposition: [name]), one methodologist (Proposition: [name]), and one statistician from Australia (Proposition: [name]).

Data will be sent to the DSMB every 24 weeks. A summary of SAEs, grade 3/4 AEs and laboratory toxicities, and AEs leading to discontinuation will be provided on a monthly basis.

There will be a single, un-blinded, interim safety and efficacy analysis and review meeting after the last participants has completed 48 weeks of follow-up. The following data will be reviewed:

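### The low-phosphate grades in Appendix 22.6 overlap the Melbourne normal range, so in-range results could be coded as Grade 2 or, rarely, Grade 3 adverse events

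*Combined protocol and SAP*

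**What the plan says.** Phosphate belongs to the biochemistry panel in Section 11.2, introduced with "Routine laboratory assessments for safety and tolerability will be performed including". The flow chart in Section 5 schedules biochemistry at every visit. Section 11.2 adds that "local laboratory reference ranges will apply (see appendix 22.3 and 22.4"). Appendix 22.3 lists phosphate as 0.6 to 1.30 mmol/L; Appendix 22.4, for the Swiss sites, lists 0.8 to 1.5.

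Section 13 states that "AEs and SAEs will be categorised and recorded as per the modified Division of AIDS table for grading the Severity of Adverse Events". In that table (Appendix 22.6, Chemistries) the row "Phosphate, serum, low" sets Grade 1 from 0.81 mmol/L up to the LLN, Grade 2 at "0.65 – 0.80 mmol/L", Grade 3 at "0.32 – 0.64 mmol/L" and Grade 4 below 0.32. Only the upper end of Grade 1 depends on the local laboratory. The table's instructions also say that a laboratory value lying between a normal limit and Grade 1 is left ungraded.

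The grades feed two outputs. The first secondary outcome in Section 7.2 is "The rate of adverse effects (symptomatic and biochemical) between the two treatment arms", which Section 17 summarises by frequency and percentage. For the DSMB, Section 15 says: "A summary of SAEs, grade 3/4 AEs and laboratory toxicities, and AEs leading to discontinuation will be provided on a monthly basis".

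**The concern.** A severity scale for a low laboratory value would normally begin at or below the lower limit of normal. Here the Grade 2 and Grade 3 bands reach above the Melbourne LLN, so one result can be normal under Appendix 22.3 and moderate or severe under Appendix 22.6. Melbourne is planned to supply 72 of the 102 participants (Section 4), so most phosphate results fall under the affected range.

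At stake is the meaning of the biochemical adverse-effect rate and of the monthly grade 3/4 and laboratory toxicity summary. Two graders could code a Melbourne value of 0.70 differently, and both could cite the plan.

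**Working it through.** The plan states no rate or count on this point that could be reproduced. The check compares intervals and then gives an illustration of size.

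**Inputs**
- Melbourne range 0.60 to 1.30 (Appendix 22.3); Swiss range 0.80 to 1.50 (Appendix 22.4). Limits printed to one decimal are read as 0.60, 0.80 and 1.50.
- Grade bands from the low-phosphate row of Appendix 22.6.

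**Step 1: grade every in-range value in steps of 0.01 mmol/L** (71 values per range)

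| | Melbourne | Swiss |
|---|---|---|
| In range and Grade 3 | 0.60 to 0.64 (5 values) | none |
| In range and Grade 2 | 0.65 to 0.80 (16 values) | 0.80 only (1 value) |
| In range and ungraded | 0.81 to 1.30 (50 values) | 0.81 to 1.50 (70 values) |
| Grade 1 interval | 0.81 to <0.60: empty | 0.81 to <0.80: empty |
| Grades possible below the LLN | 3 and 4 | 2, 3 and 4 |

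In Melbourne, 16 + 5 = 21 of 71 in-range values carry a grade. No in-range value is Grade 4 at either location.

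**Step 2: test the instruction on values below Grade 1.** There are two readings.
- *Results too mild to reach Grade 1*, as its label suggests. It then does not touch the Grade 2 and Grade 3 cells, and the overlap stands.
- *Literally, anything between the LLN and Grade 1.* In Melbourne this exempts 0.60 to 0.80, the disputed zone. The whole printed Grade 2 band then becomes unreachable there, and grading jumps from none at 0.60 to Grade 3 at 0.59.

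The row is defective on either reading.

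**Step 3: size, for illustration only.** The documents give no phosphate distribution. Assume a normal distribution with mean m and SD s, and 72 participants × 5 post-baseline visits (weeks 12, 24, 48, 72, 96) = 360 draws, with no drop-out. With results rounded to 0.01, take

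P(in range, Grade 2) = Φ((0.805 − m)/s) − Φ((0.645 − m)/s)

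P(in range, Grade 3) = Φ((0.645 − m)/s) − Φ((0.60 − m)/s)

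The base case treats the Melbourne range as the central 95%: m = (0.6 + 1.3)/2 = 0.95 and s = 0.7/3.92 = 0.179.
- Grade 2: Φ(−0.812) − Φ(−1.708) = 0.2084 − 0.0438 = 0.165; × 360 ≈ 59.
- Grade 3, in range: Φ(−1.708) − Φ(−1.960) = 0.0438 − 0.0250 = 0.019; × 360 ≈ 7.

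| m, s | In range, Grade 2 | In range, Grade 3 |
|---|---|---|
| 0.95, 0.179 | 59 | 7 |
| 1.05, 0.18 | 27 | 2 |
| 1.05, 0.15 | 17 | 1 |

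These are draws, not participants or events. Repeat values in one person are correlated and may be recorded as one event or none.

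**The case against.** The strongest reply is that Section 13 grades adverse events, not laboratory values. It defines an event as something untoward or unfavourable, and it excludes pre-existing conditions unless they change in frequency or severity. An investigator could reasonably decide that a normal phosphate result is not an event, and nothing orders automatic grading of every result. This stands: a reader might infer that normal results *would* be counted, but the documents support only that they *could* be. The gap remains because no rule excludes them, and Section 15 lists laboratory toxicities alongside adverse events without saying how one is identified.

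The DSMB effect is also narrow. Only 0.60 to 0.64 is both normal and Grade 3. A reader might take all Grade 3 phosphate results to be false. In the base case there would be about 16 (0.044 × 360), but about 8 to 9 of them lie below the Melbourne LLN and are genuinely low.

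A reader might further infer that the overlap could mimic a drug effect or trigger action. No stopping rule in Section 15 and no withdrawal criterion in Section 9.4 uses phosphate; the laboratory trigger there is CK or transaminase. Allocation is 1:1, blinded and stratified (by country in Section 8.1, by centre in Section 12.4), so spurious counts should fall on both arms alike. The documents show no route to bias in one direction.

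**Conclusion.** The conflict is real and follows from the plan's own figures without any assumption: Melbourne values of 0.60 to 0.80 mmol/L are normal in Appendix 22.3 and Grade 2 or 3 in Appendix 22.6, Grade 1 is empty at both stated LLNs, and the table's instructions do not resolve it. The consequence is modest: possible extra Grade 2 counts, a few possible extra Grade 3 counts, and inconsistent coding in a descriptive safety summary. The primary endpoint is untouched.

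The illustrative 17 to 59 Grade 2 and 1 to 7 Grade 3 in-range draws depend on the assumed distributions, on no drop-out (the plan expects 15%) and on every draw being graded. They show scale and do not predict event counts.

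**What to change.** 1. Reconcile Appendices 22.3 and 22.4 with the low-phosphate row and the values-below-Grade-1 instruction in Appendix 22.6 before grading. The sponsor must decide which figures hold.
2. State one explicit rule, applied at all sites, on whether a result inside the local reference range is graded or counted as a laboratory toxicity. The same sentence would cover glucose: Melbourne's range is 3.8 to 7.7 mmol/L, while fasting high glucose is Grade 1 from 6.11 and Grade 2 from 6.95.
3. Re-derive any existing phosphate grades from the stored laboratory values, and use them in the DSMB summaries and the secondary adverse-effect rate.

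Rescaling the grades to fractions of the local LLN, an option the fibrinogen row offers, is not recommended here. It would choose one cut-off over another, and it would grade the same concentration differently by country: 0.60 is at the Melbourne LLN but is 0.60/0.80 = 0.75 of the Swiss LLN.

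The cost is a correction to the appendices, one added sentence and a re-derivation from data already held. No extra tests or visits are needed.
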